3	-1.99302	1.99302	0.046259	0.037903	0.050000	0.382549	0.800000
Details whe	en Spending = C)'Brien-Flem	ning, N1 = 68	, N2 =68, P1	= 0.08, P2 =	0.26	
	Lower	Upper	Nominal	Inc	Total	Inc	Total
Look	Bndry	Bndry	Alpha	Alpha	Alpha	Power	Power
1	-3.71030	3.71030	0.000207	0.000207	0.000207	0.018650	0.018650
2	-2.51142	2.51142	0.012025	0.011890	0.012097	0.398801	0.417451
3	-1.99302	1.99302	0.046259	0.037903	0.050000	0.382549	0.800000
Details whe	en Spending = C)'Brien-Flem	ning, N1 = 75	, N2 =75, P1	= 0.09, P2 =	0.26	
	Lower	Upper	Nominal	Inc	Total	Inc	Total
Look	Bndry	Bndry	Alpha	Alpha	Alpha	Power	Power
1	-3.71030	3.71030	0.000207	0.000207	0.000207	0.018650	0.018650
2	-2.51142	2.51142	0.012025	0.011890	0.012097	0.398801	0.417451
3	-1.99302	1.99302	0.046259	0.037903	0.050000	0.382549	0.800000

Addendum Nov 16, 2016

At the second interim analyses, we had enrolled 100 patients (2/3 of the 150 total sample size), of whom 88 (12% attrition rate) patients were eligible for analysis (please, see Interim Analyses report for details). This attrition rate was similar to the lowest anticipated attrition rate (see first table above). Yet we noticed several important differences regarding the assumptions used to estimate the sample size. In brief, the cohort enrolled based on the entry criteria (field systolic blood pressure, SBP<70mmHg or SBP <90mmHg AND heart rate>108bpm) was less severely injured than anticipated (as measured by base deficit, INR and TEG G) and had lower mortality than anticipated.

Variable	Anticipated (sample size/power analyses assumptions)	COMBAT group A	COMBAT group B
INR	1.47	1.32	1.38
INR>1.5	24% to 36% *	18%	16%
Base deficit (mEq/L)	5.15	11.2	9.2
TEG G dynes/cm ²	4.9	7.3	7.5
Mortality	26%	12%	13%

* {MacLeod, 2003 #1415;Maegele, 2007 #905;Niles, 2008 #4410}

In addition, a slightly lower proportion of patients required transfusions (55% of group A, 61% of group B) compared to our anticipated proportion based on trauma registry data encompassing the period of January 2009-December 2011 (3 years) and excluding patients who died within 10 minutes of arriving at ED (64%).

Although we enrolled a cohort with less physiologic and coagulation derangement than anticipated, which decreased our statistical power to detect differences in the primary and secondary outcomes, we detected some promising trends, as follows:

[figure not shown]

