1) Group B experienced larger improvement in coagulopathy as measured by fibrinolysis from Field to ED (one of our secondary objectives, see below): as demonstrated by a repeated measures mixed linear model, the interaction between time and randomization approached significance, suggesting that group assignment modified the temporal trends of fibrinolysis as

measured by rTEG Ly30. Limiting the model to patients who presented in the Field in severe shock further increased the significance.

Linear Models for Repeated	ear Models for Repeated Measures including only Field and ED times for TEGs											
Model for LY30		ALL PATIE	ENTS		SEVERE SHOCK ONLY (Field SBP<=70mmHg)							
	Beta	SE	P-VALUE	Beta	SE	P-VALUE						
Intercept	6.7484	2.8959		6.2593	3.7915							
Time (ED, Field)	1.5018	2.9601	0.2528	4.9843	4.1149	0.5087						
Randomization (groups A, B)	3.3722	4.165	0.8321	7.0309	5.9547	0.9767						
Randomization*time (Interaction)	-8.1625	4.4787	0.0721	-14.3628	6.5971	0.0348						

2) Toleration of longer time to RBC **without** any adverse event, which was another of our secondary objectives (an objective of major importance to the military, and consequently to our funder, the Dept. of Defense)

There seemed to be a difference in time from injury and from ED arrival to the first required RBC favoring group B, who tolerated longer time without increasing mortality or any other adverse event. A survival analysis, however, did not reach significance.

More important, there has been no increase in adverse events or any suggestion of harm to enrollees and enrollment has been on target.

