There are several explanations for the differences in the expected and observed values. First, for the most common injury mechanisms, the case-fatality rate is decreasing in our trauma center ([name] et al. JAMA, 2016). Second, the wide use of TEG-guided hemostatic resuscitation in our institution has been associated with a dramatic decrease in post-injury mortality (Gonzalez, Ann Surg, 2016). In addition, our findings are not isolated. A recent multicenter RCT (Connelly et al., JAMA Surgery, 2016) also noted that the patients enrolled were less severely injured than anticipated based on previous experiences. Given the time required to establish such intense trials, usually one to two years, the assumptions used in the calculation of the sample size can understandably become outdated. This has prompted proposals of alternative designs for RCTs, such as adaptive and Bayesian RCTs as recently described by an NIH-funded workshop (Coffey et al. Clinical trials, 2012).

Based on the explanations above, we propose a continuation of the trial to increase sample size and make it adequate to detect differences in the proposed outcomes (mortality, admission acidosis and coagulation, hemorrhage as well as requirement for blood products), as follows:

Hypothesis for primary endpoint above: 28-day mortality will be significantly higher in control patients compared to experimental patients.

With 80% power, 95% confidence and assuming 12% mortality rate in the control group (based on the second interim analyses data), with 5 interim analyses (4 interim and 1 final, of which 3 already occurred), we will require 112 patients in each group (assuming the attrition rate observed in this RCT of 12%) to detect a difference of 10 percent points. This results in a total of 224 patients, which corresponds to an increase of 74 patients over the current sample size of 150 patients. See below the significance level for the 5 analyses.

Spending = O'Brien-Fleming, N1 = 112, N2 =112, P1 = 0.12, P2 = 0.02, Continuity Correction.

		Lower	Upper	Nominal	Inc	Total	Inc	Total
Look	Time	Bndry	Bndry	Alpha	Alpha	Alpha	Power	Power
1	0.20	-4.87688	4.87688	0.000	0.000	0.000	0.00015	0.000
2	0.40	-3.35695	3.35695	0.001	0.001	0.001	0.05885	0.059
3	0.60	-2.68026	2.68026	0.007	0.007	0.008	0.25750	0.317
4	0.80	-2.28979	2.28979	0.022	0.017	0.024	0.28890	0.605
5	1.00	-2.03100	2.03100	0.042	0.026	0.050	0.19460	0.800

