Mixed linear modeling with SAS Proc Mixed allows for incomplete data, thus all observed points will be used in the analysis. Missing data in temporal trends will be dealt with differently depending on the reason for missing. If MAR (loss to followup, withdrawn from study), multiple imputation methods will be used, as recommended by the Panel on Handling Missing Data in Clinical Trials. However, as described in previous sections, a major reason for missing data in these cases is early death, resulting in data MNAR, for which we will use the same approach to deal with the missing data as described for the secondary endpoints.

A similar analysis will be carried out for temporal trends in Proteomic Profile, Actin and Neutrophil Elastase inhibitors.

5. Blood components transfusion in the first 12 hours postinjury

a. Packed Red Blood Cells (RBC) volume

1. **Hypothesis:** The volume of RBC transfused in the first 12 hours postinjury will be larger among control patients compared to the experimental group patients.

b. Plasma volume

- **1. Hypothesis:** The volume of plasma transfused in the first 12 hours postinjury will be larger among control patients compared to the experimental group patients.
- 2. Statistical test for a.1 and b.2: These variables are usually non-normally distributed, thus the Wilcoxon non-parametric test will be used to compare the two groups and median/interquartile range will be used to express data central tendency and dispersion. If adjustment for covariates is needed, we will follow the procedure described for continuous, not normally distributed variables. Overall experiment error will be adjusted for the number of blood transfusion parameters being analyzed using the Bonferroni method.
- c. **Time to first RBC:** This is a variable of high importance for DOD, which leads to direct application in war theater trauma.

- **1. Hypothesis:** Time to the first RBC will be longer among patients in the experimental group compared to control patients.

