- 2. Statistical test: Kaplan Meyer curves will be compared using SAS PROC LIFETEST, which provides nonparametric k-sample tests based on weighted comparisons of the estimated hazard rate of the individual population under the null and alternative hypotheses. A variety of tests can be specified, of which we will use the Wilcoxon test (which places more weight on shorter survival times) and the log-rank test (which privileges longer survival times). SAS PROC LIFETEST also constructs statistics to test for association between covariates and the lifetime variable through rank tests for the association of survival time with covariates

H. Missing data prevention and treatment procedures:

We will follow the recommendations for prevention and treatment procedures outlined in the recent report by the National Research Council Panel on Handling Missing Data in Clinical Trials.⁸⁴ Missing data prevention is crucial in the primary endpoint to avoid any reduction in statistical power and the need for statistical analyses to account for the missing data. To minimize bias by missing data, research coordinators will collect data on the primary and secondary endpoints of all patients who were randomized in the field (including vital status at day 28 postinjury), including data on those patients who did not complete the protocol or were excluded for protocol violations or other reasons. Patients who withdraw from the study will be asked to allow research coordinators to collect SOC data from their medical record and, at a minimum, to provide contact information (and permission to be contacted) for verification of the primary endpoint mortality.

Based on previous trials in our institution, we predict that mortality will be missing due to loss of follow up in less than 2% of the sample. This is comparable to the loss to follow-up observed in the ROC trial (2 out 895 field-randomized patients). Several prevention procedures are in place to prevent missing data in our institution. At least two other data collection mechanisms (in addition to the COMBAT trial) will be capturing data from these patients: the Trauma Registry and the COMBAT/Trauma Activation database, which include information on the primary and secondary endpoints for COMBAT-eligible patients.

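### The 12-hour transfusion volume test ranks early deaths as low use, and IV.G.5 gives no rule for death in its volume or time-to-first-RBC analyses

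*Combined protocol and SAP*

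**What the plan says.** Section IV.G.5 lists three transfusion outcomes as exploratory analyses.

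- **12-hour RBC and plasma volume.** For red cells the hypothesis is that "The volume of RBC transfused in the first 12 hours postinjury will be larger among control patients"; plasma volume has the same form. These variables are expected to be non-normal, "thus the Wilcoxon non-parametric test will be used to compare the two groups". On multiplicity, "Overall experiment error will be adjusted for the number of blood transfusion parameters being analyzed using the Bonferroni method".
- **Time to first RBC.** The hypothesis is that "Time to the first RBC will be longer among patients in the experimental group compared to control patients". For the analysis, "Kaplan Meyer curves will be compared using SAS PROC LIFETEST, which provides nonparametric k-sample tests"; the log-rank and Wilcoxon tests are named. No time origin, end of window or censoring rule is given.

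IV.G.5 has no rule for a patient who dies before a first RBC or inside the 12 hours. Other sections have death rules, but none reaches IV.G.5:

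- IV.G.3 scores death before day 28 as zero ventilator-free days.
- IV.H treats data missing because of death as informative. It sets out survivor analyses, composites with 1-hour death, and imputation, but only for secondary endpoints 2 to 4. IV.G.4 carries that approach to the temporal trends.
- For 24-hour mortality, IV.H only says that missing death times are censored.

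The November 2016 addendum in IV.E lists time to first RBC among promising trends, describing group B as patients "who tolerated longer time without increasing mortality or any other adverse event". It adds that a survival analysis was not significant.

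**The concern.** Death ends the accrual of transfused units and rules out a later first unit. When lower volume and longer time count as success, a patient who dies after little or no blood can score as a good result. Between arms this matters only if early deaths differ. In that case the comparison mixes need for blood with time alive to receive it. The error can run either way: it can credit the arm with more deaths with lower use, or hide a real saving in the arm with fewer deaths.

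The outcomes are exploratory but they carry weight. Reduced transfusion is part of study aim 3, IV.G.5 calls time to first RBC highly important to the funder, and IV.I.1(c) lets significant exploratory results count towards calling the therapy promising. Early death is also common on the plan's own figures. IV.G.1 puts control mortality at 19% to 26% by 24 hours, and IV.E assumes 26% by 30 days. At the lower figure, 19/26 = 73% of deaths fall in the first day.

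**Working it through.** The plan gives no sample size, power or event count for IV.G.5, so there is no figure to reproduce. The check is a simulation in which the arms have **equal** need for blood, so every significant result is false.

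**Inputs from the documents**
- Sample size: 112 per arm with 12% attrition (addendum, IV.E). 112 × 0.88 = 98.6, so 99 per arm.
- Share transfused at the second interim: "a slightly lower proportion of patients required transfusions (55% of group A, 61% of group B". 58% is used, the midpoint: (55 + 61)/2.
- Interim mortality 12% and 13% by group. The addendum plans by "assuming 12% mortality rate in the control group (based on the second interim analyses data" and looks for a 10-point difference. An early-death contrast of 12% v 2% has that same gap.

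**Assumptions not in the documents**
- Latent time to first RBC is exponential with mean 0.5 to 2 h.
- Hourly RBC use is gamma-Poisson, averaging about 5.7 units per patient if nobody dies early.
- Early deaths occur only among patients who need RBC, uniformly from 0.25 h to an upper limit of 1 to 3 h.
- 1,500 trials per setting, two-sided 0.05 without Bonferroni. The simulation standard error at a 10% rate is √(0.10 × 0.90/1500) = 0.8 points.

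**Results, 12% v 2% early deaths with the excess in the plasma arm.** Entries are the percentage of trials that falsely favour plasma (nominal 2.5%).

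| Analysis | mean 1 h, deaths to 3 h | 0.5 h, 3 h | 2 h, 2 h | 1 h, 1 h |
|---|---|---|---|---|
| 12-h volume, Wilcoxon as planned | 11.1 | 9.7 | 16.1 | 16.1 |
| Log-rank, deaths censored at death | 3.8 | 3.1 | 5.9 | 6.5 |
| Log-rank, deaths coded RBC-free to 12 h | 4.9 | 3.4 | 10.5 | 10.7 |
| Log-rank, first RBC or death | 1.7 | 2.7 | 1.4 | 2.1 |
| 12-h volume, death as worst rank | 0.1 | 0.5 | 0.3 | 0.3 |

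- *Volume shift.* In the first setting mean volume is 4.69 v 5.56 units, a spurious saving of 0.87. Across settings the mean Z is -0.62 to -1.00.
- *Other gaps.* A second set of runs at 12% v 2-4% gave about 6-10% for the planned volume test, hence the overall range of 6-16%.
- *Reversed.* With 2% in the plasma arm and 12% in control, the volume test falsely favours control in 10.8% to 16.5%.
- *Equal early deaths* (0%/0% or 5%/5%). All tests are near nominal: 4.5% to 5.8% two-sided.

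**Kaplan-Meier curve.** With constant hazards of 0.08/h for RBC and 0.05/h for death (assumed):
- 1-KM at 12 h = 1 - exp(-0.08 × 12) = 61.7%.
- Cumulative incidence = (0.08/0.13) × [1 - exp(-0.13 × 12)] = 48.6%.

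Read as the share transfused, 1-KM is 13.1 points too high here.

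**Gray's test as an alternative.** Separate runs used 99 per arm, 58% needing RBC, mean 1 h, deaths at 0.25-2 h and 800 trials. The percentages falsely showing less RBC in the arm with more deaths were:

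| Early deaths | Log-rank, deaths censored | Gray's test |
|---|---|---|
| 12% v 4%, among those needing RBC | 3.5 | 4.6 |
| 12% v 2%, among those needing RBC | 4.1 | 6.6 |
| 12% v 4%, independent of need | 2.2 | 3.8 |

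Gray's test is the more distorted in each case. Deaths lower the cumulative incidence of RBC directly.

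**The case against.** A reader might infer that Kaplan-Meier and the log-rank test themselves make the arm with more deaths appear to tolerate longer without blood. The documents do not support that. They state no censoring rule, so a wrong one cannot be attributed to them. With death censored, the log-rank test is a legitimate comparison of cause-specific hazards and was near nominal above. The gap between 1-KM and cumulative incidence lies within an arm. If 58% need RBC and 4%, 8% or 12% die first, 1-KM stays at 0.58 while cumulative incidence falls to 0.561, 0.541 and 0.522. The Kaplan-Meier estimate therefore gives the arm with more deaths no advantage. This part of the objection stands, and it limits the time-to-RBC point to an unstated rule and a curve that can be misread.

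A reader might also infer that the interim trend in time to first RBC comes from early deaths. That is not shown. Mortality was 12% and 13%, the addendum read the trend beside mortality, and its survival analysis was not significant. Deaths before first RBC by arm are not reported, so the question cannot be settled either way.

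It is fair, too, that a 12% v 2% gap in early deaths is severe when total interim mortality was 12-13%, and that patients in asystole or given CPR before randomization are excluded. Mortality is analysed separately at 24 hours and 28 days, and the DSMB sees it. Bonferroni would lower the error rates, though it would not remove the shift in Z. Worst-rank scoring changes the question: in the table's settings it ranked the arm with more deaths significantly worse in 9.3% to 10.8% of trials, which is mortality showing through. None of this supplies a death rule for 12-hour volume.

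**Conclusion.** The omission is real, and it matters most for 12-hour volume. With equal need and early deaths of 12% v 2-4%, the planned Wilcoxon test favours the arm with more deaths in roughly 6-16% of trials, against a nominal 2.5%. The size depends on the assumed gap, on when deaths and first units occur, and on deaths falling among patients who need blood. With balanced early deaths there is no between-arm bias. If plasma prevents early death, the error works against plasma and would hide a transfusion benefit.

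For time to first RBC the distortion is small if deaths are censored at death (about 2% to 6.5%). It can reach about 11% if they are coded RBC-free, and the plan does not say which applies.

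The primary endpoint is unaffected and no bias is shown in the interim data. This is an inexpensive improvement to exploratory analyses that can feed the judgement that the therapy is promising. Plasma volume is cut short by death in the same way, but it was not simulated.

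**What to change.** Keep the planned tests and add the following to IV.G.5:

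1. For 12-hour volumes, a Wilcoxon analysis that gives death within 12 hours the worst rank.
2. For time to first RBC, a statement that deaths are censored at the time of death in the log-rank test, with the time origin and window given in the same sentence.
3. A composite analysis of time to first RBC or death.
4. Cumulative incidence curves of first RBC with death as a competing event, for description only. Gray's test should not be used as the remedy.
5. A table of deaths before first RBC and deaths within 12 hours, by arm.

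No new data are needed: IV.C.1 already records blood products hourly and the time of death. The cost is a little more analysis. The worst-rank and composite results mix mortality with transfusion use, so they should be read beside the planned tests and not replace them.

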Based on the interim analyses, a proposed new sample size is: with 80% power, 95% confidence and assuming mean admission lactate=5 mg/dL with standard deviation of 2 in the control group (based on the second interim analyses data), with 5 interim analyses (4 interim and 1 final, of which 3 already occurred), we will require 112 patients in each group (assuming the attrition rate observed in this RCT of 12%) to detect a difference of 1 mg/dL between the two mean lactates. This results in a total of 224, which corresponds to an increase of 74 patients over the current sample size of 150 patients.

G. Exploratory analyses

- Exploratory analysis 1: 24-hour mortality Based on the control arm of the recent ROC trial⁶⁷ and our trauma registry data, the control group 24-hours mortality is estimated to be between 19% and 26%.
 - a. **Definition:** 24-hours mortality is defined as death within 24 hours post injury (death of any cause). Research coordinators will verify the vital status of all patients 24 hours postinjury and determine the time of death in relationship to injury.
 - b. **Hypothesis:** 24-hour mortality will be significantly higher^{***} in control patients compared to experimental group patients.
 - c. Statistical test: Logistic regression will be used to compare the 24-hour mortality in the two groups. Statistical significance will be evaluated at each interim analyses for the primary outcomes and p-values, as well as 95% and 99% confidence intervals will be reported to the DSMB for analyses. If adjustment for pre-defined confounders is needed, we will use the above-defined method for categorical, binary variables. Time from injury to death will be evaluated using the Kaplan Meyer curves, which will be compared using SAS PROC LIFETEST. We will use the Wilcoxon test (which places more weight on shorter survival times) and the log-rank test (which privileges longer survival times). SAS PROC LIFETEST also constructs statistics to test for

^{***} Although the hypothesis is worded as "lower", all tests will be two-tailed to control for differences in either direction (higher or lower than the other group).

association between covariates and the lifetime variable through rank tests for the association of survival time with covariates, if there are potential confounders detected using the above-described procedures.

2. Pre-planned subgroup analyses:

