Because the secondary endpoints 2, 3 and 4 (admission coagulopathy, acidosis and clot strength) are obtained at 30 minutes postinjury in all trauma activation patients, we anticipate very few missing data. The main and most complicated reason for missing data in these secondary endpoints is death before test was obtained. These data are clearly "missing not at random" (MNAR), as they are likely to represent the most injured patients and those more likely to have abnormal test values. This survivor-bias plagues emergency and trauma research and it is difficult to manage in the analysis period. ¹⁰⁹⁻¹¹¹ As recommended by the Panel on Handling Missing Data in Clinical Trials, missing data both due to death and related to death must be treated as a special case. ⁸⁴ We will proceed as follows for these analyses: 1) the primary analysis will focus on all patients with complete data; 2) the second analysis will focus on those who remained alive in either group; 3) a third approach will fold death occurring within 1-hour between ambulance arrival at scene into the two binary endpoints 2, 3 and 4 to form composite outcomes (admission coagulopathy or 1-hour death; admission acidosis or 1-hour death). For the continuous secondary endpoints 2, 3, and 4, we will limit the analyses to approaches 1 and 2 and as a third approach, multiple imputations will be used.

Missing data for the variables chosen to assess effectiveness of randomization are anticipated to be less than 5% given the mechanisms described above. For the variables MAR with >5% missing data, we will use the multiple imputation method. ^{81, 84} If the variable is MNAR, the missing indicator method, as proposed by [name] et al., which is equivalent to the inverse probability weighting method, will be employed. In brief, the variable is categorized in missing, normal value and abnormal value, using established cutoffs for normal and abnormal values.

Missing data procedures for exploratory analysis 1: By the very nature of the study, missing data for this outcome (24-hour mortality) as a binary outcome (death yes or no) is likely to be null; while missing data for time from injury to death within 24 hours can be missing, which will be censored in the above-described survival analysis.

I. Trial assessment

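### Known deaths within 24 hours whose time of death is missing are censored, so they drop out of the exploratory survival comparison of early mortality

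*Combined protocol and SAP*

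**What the plan says.** Section IV.G, exploratory analysis 1, sets out two analyses of early death. The first is binary: "Logistic regression will be used to compare the 24-hour mortality in the two groups". The second is time to event: "Time from injury to death will be evaluated using the Kaplan Meyer curves, which will be compared using SAS PROC LIFETEST". The tests follow: "We will use the Wilcoxon test (which places more weight on shorter survival times) and the log-rank test". Research coordinators are to check vital status at 24 hours and "determine the time of death in relationship to injury".

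The last paragraph of Section IV.H gives the missing-data rule. It says that missing data for 24-hour mortality "as a binary outcome (death yes or no) is likely to be null", and then, of the time to death, "missing data for time from injury to death within 24 hours can be missing, which will be censored in the above-described survival analysis". It gives no censoring time, and nothing in it keeps a known death as an event.

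**The concern.** The sentence contrasts a death status that is known for nearly everyone with a death time that may not be. The patients it covers are therefore known deaths. A censored record adds no event to a Kaplan-Meier curve or to a log-rank or Wilcoxon statistic. It says only that the patient was alive when last observed and then had the same prospects as others still at risk. Here the patient is known to be dead by 24 hours, so the censoring is informative by construction.

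Three things follow:

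- Two analyses of one outcome in the same patients would count different numbers of deaths.
- If missing times are unequal between arms, the survival comparison shifts towards the arm that loses more deaths.
- Because no censoring time is stated, two programmers could implement the rule differently.

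The analysis is exploratory but is used. Section IV.G sends the 24-hour mortality results to the DSMB at each interim analysis. Section IV.I.1.c makes significant exploratory findings one route to calling the therapy promising, and Section IV.I.2.a puts exploratory results in the early-stopping materials. Earlier in Section IV.H, for the admission laboratory endpoints, the plan itself accepts that death-related missing data need separate handling. This rule does the opposite.

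**Working it through.** The plan states no power, event count or missing rate for this analysis, so it has no figure to reproduce. The check asks what the rule does to the estimate and to the test.

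**Inputs from the documents.** 112 patients per arm (November 2016 addendum, Section IV.E); expected control 24-hour mortality of 19% to 26% (Section IV.G).

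**Assumed.** One to three deaths with a missing time in one arm; censoring at time 0 or at 24 hours, since the plan does not say which.

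**Effect on the Kaplan-Meier estimate.** Let an arm have N patients and D deaths by 24 hours, with everyone else followed to 24 hours.

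- All deaths counted: mortality = D/N.
- k deaths censored at 24 hours: (D − k)/N.
- k deaths censored at time 0: (D − k)/(N − k).

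| N = 112 | k = 0 | k = 1 | k = 2 | k = 3 |
|---|---|---|---|---|
| D = 21 (19%), censored at 24 h | 18.8% | 17.9% | 17.0% | 16.1% |
| D = 21, censored at time 0 | 18.8% | 18.0% | 17.3% | 16.5% |
| D = 29 (26%), censored at 24 h | 25.9% | 25.0% | 24.1% | 23.2% |
| D = 29, censored at time 0 | 25.9% | 25.2% | 24.5% | 23.9% |

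One death costs 1/112 = 0.89 points if censored at 24 hours. Censored at time 0 it costs (N − D)/[N(N − 1)]: 91/(112 × 111) = 0.73 points for D = 21, and 83/(112 × 111) = 0.67 points for D = 29. The range is therefore about 0.7 to 0.9 points per death. The logistic regression still works from D/N.

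**Effect on the log-rank statistic.** Mean Z over simulated data sets with 112 per arm and uniform death times, the lost deaths all being in the plasma arm (negative Z favours plasma):

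- 21 v 21 deaths: Z moves from 0 to between −0.14 and −0.17 with one lost death, and to between −0.44 and −0.53 with three.
- 21 v 11 deaths: Z moves from about −1.9 to about −2.1 with one lost death.

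One death matters to significance only when the result already lies near the boundary.

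**Effect on the error rate.** Simulated trials with 99 per arm (112 × 0.88 = 98.6), true 24-hour mortality of 10% in both arms and log-rank |Z| > 1.96. That gives about 9.9 deaths per arm. The 10% is an assumption below the plan's 19% to 26%, chosen because the addendum reports overall mortality of only 12% and 13% in the two groups.

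| Death times missing, control v plasma | Deaths lost, about | False plasma harm |
|---|---|---|
| none | 0 v 0 | 2.5% (nominal) |
| 10% v 0% | 1 v 0 | about 4% |
| 40% v 10% | 4 v 1 | about 10% to 12% |

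Reversing the arms gives false benefit at the same rates. The Wilcoxon test was not simulated.

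**The case against.** The sentence is badly worded. It might mean only that patients with no death within 24 hours, the survivors, are censored, which is ordinary practice. This does not fit the text: a survivor has no death time to be missing, and the sentence stands among the missing-data rules, directly after the statement that death status is known.

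The stronger objection concerns size, and it stands. Time of death is a collected item (Section IV.C.1.c), and coordinators are asked to establish it, so few times should be missing. The binary 24-hour analysis keeps every death. The DSMB is to receive a description of missing data (Section IV.I.2.a), so recoded deaths should be visible.

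A reader might infer three further things that the documents do not support:

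- *That times will be missing because injuries are often unwitnessed.* No section says so. Injury also precedes randomisation, and the cooler contents are concealed until the cassettes are opened, so an unknown injury time could not be caused by the assigned arm.
- *That 20% to 40% of death times will be missing, or that the loss will differ greatly by arm.* The documents give no such rates, so the 40% v 10% line is a stress test and not a forecast.
- *That the clock should start at randomisation instead of injury.* That is a separate design preference. It does not recover a missing death time, and applied generally it would also alter the analysis of time to first red-cell transfusion.

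**Conclusion.** The rule is wrong as written: followed literally, it drops known deaths from the exploratory survival comparison and makes its 24-hour mortality disagree with the binary result. The shift in the estimate is arithmetic and holds under either censoring time. The effect on the test depends on how many death times are missing and in which arm, which the documents do not say. With about one lost death it is small; it becomes material only under stress-test rates. The error-rate figures also assume a single look at 1.96, whereas Section IV.I.1.c asks exploratory results to respect the interim boundaries (2.031 at the final analysis in the addendum).

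The primary 28-day Fisher test and the 24-hour logistic regression are untouched. Severity is minor, but the sentence should be corrected before the remaining analyses.

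**What to change.** Replace the last clause of the exploratory analysis 1 paragraph in Section IV.H with:

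*Every patient known to have died within 24 hours is an event. Where the exact time of death is unknown, it is bounded between the last time documented alive and the time death was recorded (or 24 hours); the recorded time is used in the main analysis and the interval midpoint in a sensitivity analysis. Patients alive at 24 hours are censored at 24 hours.*

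Report the number of deaths with an unknown time by arm. The time origin can stay as it is. The cost is some extra chart review to find the bounding times for the affected patients, and one sensitivity analysis.
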